6.1 Overview of Study Design

After Informed Consent is obtained, subjects will be randomized 1:1 into two groups via the block randomization method with a list held in each test setting. Standard landmarking techniques will be used in both groups to identify the procedure area. For subjects randomized to the tactile-imaging group (T), VerTouch will be used to identify an interspinous space and to place a marker, introducer, or needle. For subjects randomized to the palpation group (P), the palpation-landmarking method will be used. After marker, introducer, or needle placement, the procedure will continue in the usual manner for subjects in both groups (**Figure 6**).

A designated study observer within each setting will record the time to identify an insertion site; time to place the marker, introducer, or needle; number of insertions, re-directions, and bone contacts (counted until confirmation of spinal canal access

can be assessed); incidence of procedure success; subject's level of discomfort during landmarking; and provider's level of confidence with the identified insertion site. Total procedure time, incidence of traumatic taps, and incidence of referrals to radiology or pain management will be recorded in all settings. In anesthesiology, incidences of paresthesia, unintended dural puncture, and conversion from spinal to epidural anesthesia, will be collected for exploratory analysis, where applicable. Any usability issues or device malfunctions observed during the clinical study will also be documented.

[figure not shown]

Figure 5. Overall Study Design

Although spinal punctures in all clinical settings involve the same localization and insertion processes, there may be variations in setting, subject, and/or provider characteristics. While early VerTouch testing has not evidenced any corresponding variations in device usability and/or outcomes associated with these variations, the study is designed to capture them.

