6.3.2 Secondary Clinical Endpoint(s)

1. Incidence of first-insertion success (a case that does not require any reinsertions, but can include any number of redirections)
2. Number of redirections (any forward movement of the needle in a new direction not preceded by withdrawal from the skin, counted until confirmation of spinal canal access can be assessed)
3. Number of passes (any forward movement of the needle, calculated as the sum of insertions and redirections)
4. Incidence of first-pass success (a case that does not require reinsertions or redirections)
5. Subject discomfort during landmarking on a 100mm VAS (See Section 17.1)

6. Provider confidence with the identified insertion site on a 1-5 Likert scale (See Section 17.2)
7. Procedure success as confirmed by the following procedure-specific methods:
 - Epidural anesthesia: able to achieve a T10 or greater bilateral sensory level change to cold
 - Spinal anesthesia: able to achieve sensory blockade to surgical stimulus at level desired
 - Diagnostic and therapeutic LP: return of CSF
 - Blood patch: able to inject homologous blood into epidural space (entry confirmed by loss-of-resistance)

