6.3.3 Tertiary Endpoints

1. Localization time (time from first touch of draped patient to identification of an insertion site; for VerTouch, this is the time from device placement to movement of the applicator to the identified insertion site)
2. Insertion time (time from retrieval of marker or LA assembly until no further needle advancements are made)
3. Number of bone contacts (counted until confirmation of spinal canal access can be assessed)
4. Incidence of referral to radiology

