7.4 Clinical Procedures

7.4.1 Visit 1

Screening

At the screening visit the following activities and information will be collected:

- Informed Consent
- Physical Examination (height/weight)
- Eligibility Determination
- Randomization and Subject ID Assignment

- Demographics (gender, age, race, ethnicity)
- Relevant Medical History
- Concomitant Medications

At Treatment

At the time of treatment, the following activities and information will be collected:

- Concomitant Medications
- Pain and/or anti-anxiety medication(s) given for the procedure
- Provider level of training (e.g. resident, fellow, attending, PA, CRNA, NP)
- Provider number of years of in practice
- Provider experience (i.e. number of neuraxial procedures performed in the past 12 months)
- Provider specialty (i.e. emergency medicine, neurology, anesthesiology)
- Procedure setting (i.e. emergency medicine, neurology, orthopedic anesthesiology, obstetric anesthesiology)
- Type of neuraxial procedure (i.e. diagnostic LP, therapeutic LP, spinal anesthesia, epidural anesthesia, CSE, blood patch)
- Reason for Neuraxial Procedure (if not diagnostic LP or blood patch), such as:
 - Therapeutic LP: CSF drainage, intrathecal injection, other
 - Orthopedic procedure: total hip replacement, total knee replacement, other
 - Obstetric procedure: labor/induction, cesarean section, hysterectomy, tubal ligation, other

The subject will be treated with the device or control, per **Figure 6** below (see IFU for more detailed VerTouch steps)^[24]. Initial landmarking for vertebral level is performed by standard technique in both groups in order to identify a safe level when placing the drape to expose the procedure area.

Listed data will be recorded in source documentation, by a member of the study team designated as an observer, as they become available. The observer will also be responsible for counting needle insertions and redirections. Note that procedure success may be reported at different points within the treatment, depending on when spinal access can be confirmed for the particular neuraxial procedure.

[figure not shown]

Figure 6. Flowchart of Visit 1 treatment.

Post-Treatment

After the completion of the procedure, the following activities and information will be collected:

- Patient position (seated, lateral decubitus)

- Length, gauge, bevel (cutting, non-cutting), and type (straight, curved) of needle used

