- VerTouch workflow followed (N/A (control group), marking, introducer placement, needle placement)
- Calculation of number of re-insertions (1 less than insertions)
- Incidence of first-insertion success (1 insertion, any number of redirections)
- Calculation of number of passes (sum of insertions and redirections)
- Incidence of first-pass success (1 pass)
- Calculation of localization, insertion, and procedure times (based on start and end times)
- Incidence of traumatic tap
- Incidence of referral to radiology
- Incidence of conversion from spinal to epidural (neuraxial anesthesia only)
- Incidence of paresthesia (neuraxial anesthesia only)
- Incidence of PDPH
- Intensity of PDPH (mild, moderate, severe)
- Incidence of unintended dural puncture (epidural anesthesia only)
- Subject Discomfort Assessment
- Provider Confidence Assessment
- Adverse Event Assessment
- Upload of data from VerTouch

Post-procedure, the subject will be monitored for adverse events, adverse device effects or other reportable observations to ensure safety, entering relevant data into the eCRF. At the conclusion of the visit, the subject will be released and considered complete. After each procedure, imaging data from VerTouch will be uploaded by the designated observer to a study portal to support investigation of any anomalous finds and/or establishment of a human image database.

7.4.2 Visit 2

Visit 2 must occur at 3 ± 2 days following Visit 1. Phone, or other appropriate follow-ups will be made at Visit 2 to assess the presence and intensity of PDPH in subjects, and assess potential adverse events. At the conclusion of Visit 2, a Subject Study Exit CRF will be completed.

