7.6 Study Timetable / Schedule of Events

Table 2. Schedule of Events

Assessment	Visit 1			Visit 2
	Screening	Treatment	Post-Treatment	Follow-up
Demographics	X			
Medical History	X			
Physical Exam (Height & Weight)	X			
Inclusion/Exclusion Criteria	X			
Informed Consent	X			
Randomization	X			
Concomitant Medications	X		X	
Procedure Completion		X		
Discomfort Assessment			X	
Provider Satisfaction Assessment			X	
PDPH				X
Adverse Event Assessment			X	X
Adverse Device Effect Assessment			X	X

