8.2.1 Adjustments for Multiplicity

The study has a single primary endpoint needed for the superiority analysis. If that analysis reaches statistical significance, then the following additional hypothesis of the secondary variables will be considered sequentially such that if one analysis is statistically significant, then the next hypothesis can be evaluated to control for the Type I error for these analyses:

Additional Hypothesis 1: The null hypothesis that the binary rate of first-attempt success is the same in both groups will be analyzed using a likelihood ratio test ($H_0: p_1 = p_2$ vs $H_1: p_1 \neq p_2$ where p_1 is the success rate in VerTouch subjects and p_2 is the success rate in control subjects). The results will be considered statistically significant if the two-sided p-value is less than 0.05 and the VerTouch success rate is higher than the control rate).

Additional Hypothesis 2: The null hypothesis that the mean number of redirections is the higher in the VerTouch subjects compared to the control group using a T-test with unequal variance assumption ($H_0: \mu_1 \geq \mu_2$ vs $H_1: \mu_1 < \mu_2$ where μ_1 is the mean in VerTouch subjects and μ_2 is the mean in control subjects). The results will be considered statistically significant if the one-sided p-value is less than 0.025.

Additional Hypothesis 3: The null hypothesis that the mean number of passes is the higher in the VerTouch subjects compared to the control group using a T-test with unequal variance assumption ($H_0: \mu_1 \geq \mu_2$ vs $H_1: \mu_1 < \mu_2$ where μ_1 is the mean in VerTouch subjects and μ_2 is the mean in control subjects). The results will be considered statistically significant if the one-sided p-value is less than 0.025.

Additional Hypothesis 4: The null hypothesis that the binary rate of first-pass success is the same in both groups will be analyzed using a likelihood ratio test ($H_0: p_1 = p_2$ vs $H_1: p_1 \neq p_2$ where p_1 is the success rate in VerTouch subjects and p_2 is the success rate in control subjects). The results will be

considered statistically significant if the two-sided p-value is less than 0.05 and the VerTouch success rate is higher than the control rate).

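### As written, provider confidence in the insertion site and subject discomfort with landmarking are rated after the procedure, so a positive H6 could not be separated from how the insertion went, and H5 is open to recall effects of uncertain direction

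*Protocol*

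**What the plan says.** Protocol 6.3.2 defines the sixth secondary endpoint as "Provider confidence with the identified insertion site on a 1-5 Likert scale". The fifth is subject discomfort during landmarking. Both refer to the localization step.

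The timing is set in three places:

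- **Protocol 7.4.1, Post-Treatment.** The list opens with "After the completion of the procedure, the following activities and information will be collected" and includes "Subject Discomfort Assessment" and "Provider Confidence Assessment". Neither is in the At Treatment list.
- **Protocol 7.6, Table 2.** The discomfort row and the row "Provider Satisfaction Assessment" each have one mark, under Visit 1 Post-Treatment.
- **SAP section 6 table.** It has the same rows and marks as Table 2.

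Protocol 6.1 has the observer record "subject's level of discomfort during landmarking; and provider's level of confidence with the identified insertion site" but gives no time for either.

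In protocol 8.2.1 and SAP 8.2 the secondary hypotheses are "considered sequentially such that if one analysis is statistically significant, then the next hypothesis can be evaluated". H5 (discomfort) and H6 (confidence) are each tested at one-sided 0.025, after the primary endpoint and H1 to H4. The study is open-label.

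**The concern.** A rating of confidence in a site should be given before anyone knows how that site performed. If it is taken afterwards, a provider who needed several insertions is likely to mark confidence down, and one who succeeded at once is likely to mark it up. The rating then partly restates the insertion count, which the primary endpoint and H1 to H4 already measure.

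The gating gives this a likely direction for H6. H6 is reached only when VerTouch has already shown fewer insertions, redirections and passes, higher first-insertion and first-pass success, and less discomfort. Fixed-sequence testing controls chance error but not a bias of this kind. A biased pass on H6 would also open H7.

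The subject's rating has a related weakness, because landmarking is recalled after the insertion has been experienced. Both are formal secondary tests. Protocol 8.2 and SAP 8.1 keep only tertiary and exploratory p-values out of product labeling, so H5 and H6 are not excluded from it.

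**Working it through.** **1. Timing: the passages side by side.**

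| Place | Discomfort | Provider rating |
|---|---|---|
| 6.3.2 (what is measured) | landmarking | the identified site |
| 6.1 | recorded by observer, no time | recorded by observer, no time |
| 7.4.1 | Post-Treatment list | Post-Treatment list |
| Table 2 and SAP table | Post-Treatment mark | Post-Treatment mark, labelled Satisfaction |

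Section 7.4.1 is the direct source. The SAP table matches Table 2, so it is not independent evidence. Reading the Satisfaction row as the confidence rating is an inference, though no other provider rating is defined. No readable text schedules either rating before the needle.

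**2. The plan's own figure.** Protocol 6.4.1 states 90% power for first-insertion success at 48 per group, 81% against 50%. With mean rate 0.655:

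- z = [0.31 × √48 − 1.96 × √(2 × 0.655 × 0.345)] / √(0.81 × 0.19 + 0.50 × 0.50) = (2.148 − 1.318) / 0.636 = 1.31.
- Power is 90.4%, so the stated figure reproduces. It is used below only as a planning scenario.

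**3. What winning H1 implies.** With 24/48 successes on palpation (the plan's 50%), the likelihood ratio chi-square is 3.52 for 33/48 on VerTouch and 4.40 for 34/48. The cut-off is 3.84, so H1 needs at least 34/48. That is a difference of 10/48 = 20.8 points. If H5 or H6 is reached, the arms already differ materially in insertion experience.

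**4. Illustration of carry-over.** The documents give no rating SD and no carry-over size, so both are assumed.

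- Assume no true difference in the rating, SD 1 in each arm, and a shift of s SD for each subject whose first insertion failed.
- Spurious difference: d = s × (VerTouch success rate − 0.50).
- Noncentrality: λ = d × √(48/2) = 4.90 × d.
- Rejection if t exceeds 1.986 (one-sided 0.025, 94 degrees of freedom).

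Results for the single test, if reached, at 81% against 50% (d = 0.31 × s):

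| s (positive = towards VerTouch) | d | λ | False-positive rate |
|---|---|---|---|
| −0.5 | −0.155 | −0.76 | 0.3% |
| −0.25 | −0.078 | −0.38 | 1.0% |
| 0 | 0 | 0 | 2.5% |
| 0.1 | 0.031 | 0.15 | 3.5% |
| 0.25 | 0.078 | 0.38 | 5.7% |
| 0.5 | 0.155 | 0.76 | 11.3% |

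At the smallest winning difference (34 against 24), s = 0.5 gives d = 0.104 and 7.3%.

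These are not trial-level error rates. The chance of reaching H5 or H6 cannot be computed, because the plan states no assumptions for H2 to H4.

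**The case against.** **The timing evidence is qualified.** Section 7.4.1 says treatment follows Figure 6, the likeliest place for the order of steps within the procedure, and that figure cannot be seen. The At Treatment text says the observer records the listed data as they become available. The Post-Treatment list also holds facts known earlier, such as patient position, so it could be read as a list for completing forms. Table 2 is not a reliable clock either: it marks concomitant medications under Post-Treatment and not Treatment, while 7.4.1 lists them At Treatment. All of this stands, and it rules out saying that the sponsor certainly intends post-procedure ratings. It does not supply an earlier time. A position or needle type does not change with hindsight, but a subjective rating can, and it exists only once someone asks for it.

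**The direction is not certain for both tests.** A reader might infer that any carry-over must favour VerTouch in H5 as well as H6. The documents do not support that. A subject who has been through several insertions may recall landmarking as mild by contrast, which favours palpation and makes H5 conservative (the negative rows above).

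**The size comes from the assumption.** This is correct. An assumed shift of 0.1 SD barely moves the error rate. A reader might take 11% as the plan's error rate for H6, but nothing in the documents supports a particular value.

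**The reach is limited.** H2 requires fewer redirections, while 3.5 expects that some may still be needed with VerTouch. H6 also requires H5 to show less discomfort, while 2.1 claims only the potential for no additional discomfort. H6 may never be tested. This limits the consequence and leaves the timing fault in place.

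**Conclusion.** The concern holds for H6 on the text as written: confidence in the site is collected once its performance is known, by an unblinded provider. If H6 is reached and positive, it could not be separated from the insertion outcome, and carry-over would plausibly favour VerTouch. For H5 the rating may be coloured by the insertion, but the direction is open.

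The size is unknown for both, and the percentages above show only how the error rate responds to an assumed shift. The conclusion rests on 7.4.1 being followed literally and on Figure 6 not placing the ratings earlier. If Figure 6 does, the fault becomes a conflict between the figure and the list and tables, which still needs to be reconciled.

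A reader might infer that the main result is compromised. It is not: the primary endpoint and H1 to H4 use neither rating. The change should be made before enrolment, because a rating not taken before the needle cannot be recovered later.

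**What to change.** State the timing of each rating in 7.4.1, protocol Table 2 and the SAP section 6 table, and reconcile all three with Figure 6.

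- **Confidence.** In both arms the observer records the provider's spoken whole number from 1 to 5, once the first insertion site is identified and before the marker or local-anesthetic assembly is retrieved. State that this is the value analysed for H6, since 18.2 describes the scale as a 100 mm line. By 6.3.3 the localization clock has then stopped, and the insertion clock ("time from retrieval of marker or LA assembly until no further needle advancements are made") has not started.
- **Discomfort.** Either take it at the same step in both arms, in a way that does not require the subject to move, or keep it post-procedure and report H5 with the caveat that it is a recalled rating that cannot be separated from the insertion experience.
- **Minor corrections.** Align the Satisfaction row label with Confidence in both tables. Name one discomfort instrument, since the protocol has a 100 mm VAS and SAP 8.3.4 a 0 to 10 numeric rating scale.

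**Cost.** No new assessment or staff is needed, because the observer is already present. There is a pause of seconds before insertion, with the device held in place in the VerTouch arm. That brings a small, possibly unequal, risk of disturbing position just before the primary count begins, and a slightly longer procedure time (an exploratory endpoint). Re-landmarking after a failed insertion is not captured. Open-label expectation bias remains in both ratings.

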needle in a new direction not preceded by withdrawal from the skin, counted until confirmation of spinal canal access can be assessed)

3. Number of passes (any forward movement of the needle, calculated as the sum of insertions and redirections)
4. Incidence of first-pass success (a case that does not require reinsertions or redirections)
5. Subject discomfort during landmarking on a 100mm VAS scale
6. Provider confidence with the identified insertion site on a 1-5 Likert scale
7. Procedure success as confirmed by the following procedure-specific methods:
 - Epidural anesthesia: able to achieve a T10 or greater bilateral sensory level change to cold
 - Spinal anesthesia: able to achieve sensory blockade to surgical stimulus at level desired
 - Diagnostic and therapeutic LP: return of CSF
 - Blood patch: able to inject homologous blood into epidural space (entry confirmed by loss-of-resistance)

Tertiary Endpoints:

1. Localization time (time from first touch of draped patient to identification of an insertion site; for VerTouch, this is the time from device placement to movement of the applicator to the identified insertion site)
2. Insertion time (time from retrieval of marker or local anesthetic assembly until no further needle advancements are made)
3. Number of bone contacts
4. Incidence of referral to radiology

Safety Endpoints

1. Incidence of post-dural puncture headache (PDPH)
2. Incidence of unintended dural puncture (specific to epidural anesthesia)
3. Incidence of paresthesia during needle insertion (specific to neuraxial anesthesia)
4. Incidence of traumatic tap (results in visible blood)

aspiration)

Exploratory Endpoints:

1. Procedure time (from positioning of the patient to removal of the drape from the subject's back)
2. Incidence of conversion from spinal to epidural (specific to neuraxial anesthesia)

Statistical Methods

The primary endpoint will be analyzed using a bootstrap approach for the null hypothesis that VerTouch requires more insertions than palpation. A one-sided 0.025 p-value will be considered as the cut-off for statistical significance.

Abbreviations

2D	2-Dimensional
AE	Adverse Event
BMI	Body Mass Index
CI	Confidence Interval
CFR	Code of Federal Regulations
CRNA	Certified Registered Nurse Anesthetist
CV	Curriculum Vitae
eCRF	Case Report Form
EM	Emergency Medicine
ESI	Epidural Steroid Injection
FDA	Food and Drug Administration
GCP	Good Clinical Practice

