6.3 Evaluation Criteria / Effectiveness and Safety

6.3.1 Primary Clinical Endpoint

The number of insertion attempts (any forward movement of the needle following puncture of the skin) in the study device group as compared to the control group (palpation). Attempts are counted until confirmation of spinal canal access can be assessed.

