8.2.2 Primary Effectiveness Analysis

The study is designed to evaluate whether the use of the VerTouch device is able to reduce the number of insertion attempts to successfully access the spinal canal in a spinal puncture as compared to the conventional palpation technique. The primary hypothesis test will be performed by a bootstrap analysis resampling the cases in each group. The null hypothesis for the analysis is:

$$H_0: \mu_1 \geq \mu_2 \text{ vs } H_1: \mu_1 < \mu_2$$

Where μ_1 is the mean attempts in the VerTouch group and μ_2 is the mean for palpation.

This hypothesis will be evaluated using a bootstrap analysis with a one-sided 0.025 test to indicate statistical significance. The results will be presented for the difference in means and the associated 95% CI; and the ratio of the VerTouch mean divided by the palpation mean and the associated 95% CI.

The primary analysis will include the total insertions for each subject regardless of success on the final placement attempt.

The following supporting analyses will be performed:

- The primary analysis will be performed only for subjects who had a procedure success.
- If there are missing data, best- and worst-case imputation analyses will be performed. For the worst-case imputation, the highest observed value will be imputed in the VerTouch group and the lowest value in the palpation group. The best-case analysis reverses the pattern of imputations.
- A Wilcoxon rank-sum test will be used to evaluate the null hypothesis that median attempts are the same in both arms using a two-sided test with a p-value less than or equal to 0.05 considered significant.
- Homogeneity of the log-transformed count results will be assessed using an ANOVA with site, treatment, and site-treatment interaction terms. A p-value for the site-treatment interaction of less than or equal to 0.15 will be considered statistically significant for this analysis. The n, mean, and SD of values by study site will be provided by treatment group.
- The observed attempts will be evaluated through a t-test for unequal variances comparing the difference in the log (insertion attempts) for each group. The difference will be transformed with the exponent function to provide the ratio of the geometric mean attempts and a two-sided 95% CI for the ratio.

The following subgroups will be considered in exploratory covariate analyses:

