8.3.3 Primary Efficacy Endpoint

The primary efficacy endpoint of the study is designed to evaluate whether the use of the VerTouch device is able to reduce the number of insertion attempts to successfully access the spinal canal in a spinal puncture as compared to the conventional palpation technique. Attempts are counted until confirmation of spinal canal access can be assessed.

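### The recording rule for first-insertion and first-pass success rests on the needle count alone and needs a canal-access condition to match the endpoint's evident intent

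*Protocol*

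**What the plan says.** **Recording rule.** The post-treatment list in protocol 7.4.1 gives "Incidence of first-insertion success (1 insertion, any number of redirections" and "Incidence of first-pass success (1 pass". These are the only operational derivations of the two endpoints in the available text.

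**Endpoint definitions.** Protocol 6.3.2, repeated in the synopsis and SAP 8.3.4, has "Incidence of first-insertion success (a case that does not require any reinsertions, but can include any number of redirections" and "Incidence of first-pass success (a case that does not require reinsertions or redirections". The sample-size sections (protocol 6.4.1, SAP 5) describe the same secondary endpoint as succeeding at the first insertion.

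**Test.** Additional Hypothesis 1 (protocol 8.2.1, SAP 8.2) uses another label, "The null hypothesis that the binary rate of first-attempt success is the same in both groups", and adds no access condition. It is the first secondary tested after the primary. First-pass success is Hypothesis 4 and procedure success is Hypothesis 7, the last.

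**Primary endpoint.** Protocol 8.2.2 and SAP 8.3.3.2 are explicit: "The primary analysis will include the total insertions for each subject regardless of success on the final placement attempt". Supporting analyses restrict the primary comparison to procedure successes and to the per-protocol set, which also requires procedure success. All other results use the ITT population.

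**The concern.** The recording rule depends on the count and nothing else. A procedure that is stopped, or sent to radiology, after one failed insertion has a count of one. A programmer following 7.4.1 would therefore flag it as a first-insertion success, and as a first-pass success too if there was no redirection. A programmer following 6.3.2 could reasonably decide the opposite, because a case that failed did need another insertion. Two people could thus derive different results for the first gated secondary endpoint.

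Failed cases are foreseen. The protocol collects procedure success and radiology referral as separate endpoints, but neither feeds into the success flags. The trial is open-label and the operator decides when to stop, so abandonment could differ between arms. The success-only and per-protocol repeats apply to the primary analysis only and do not check these two endpoints.

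**Working it through.** **1. The plan's own figure.** Inputs from protocol 6.4.1: 48 per group, 50% against 81%. Two-sided 0.05 is from Hypothesis 1. The pooled rate is (0.50 + 0.81)/2 = 0.655.

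z = [0.31 × √48 − 1.96 × √(2 × 0.655 × 0.345)] / √(0.50 × 0.50 + 0.81 × 0.19) = (2.148 − 1.318)/0.636 = 1.31, so power is 90.4%.

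Exact enumeration of the likelihood ratio test gives 90.8%. The stated 90% is right on its inputs; the point here is about the definition.

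**2. Mislabelled subjects.** If a share q of an arm is abandoned after one insertion, 48q subjects are flagged wrongly: 2.4, 4.8 and 7.2 at q = 5%, 10% and 15%. These rates are assumptions, because the documents give none.

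**3. Hypothesis 1 without the gate.** Let the true rate of one insertion with access be 50% in both arms, and let q apply to VerTouch only. The flagged rates are then 0.50 + q against 0.50. Exact probability of a significant result favouring VerTouch: 2.6% (q = 0), 7.3% (5%), 16.7% (10%), 31.9% (15%).

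**4. Hypothesis 1 behind the primary gate.** 10,000 simulated trials per scenario, 48 per arm, no true effect. The count is 1 with probability 0.5, otherwise 2 plus a negative binomial with mean 1.2 and variance 2.08.
- Mean: 0.5 × 1 + 0.5 × 3.2 = 2.1.
- Variance: 0.5 × 1 + 0.5 × (3.2² + 2.08) − 2.1² = 2.25, so the SD is 1.5. Both match the plan's palpation reference.
- Only subjects needing more than one insertion can be abandoned.
- Primary: percentile bootstrap, 1,000 resamples, one-sided 0.025. Hypothesis 1 counts only if the primary is significant in the same trial.

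| Abandoned, VerTouch / palpation | All stop after one insertion | Stop at a random earlier point |
|---|---|---|
| 0% / 0% | 1.0% | 1.0% |
| 10% / 10% | 1.1% | 0.8% |
| 5% / 10% | 0.3% | 0.5% |
| 5% / 0% | 3.1% | 2.1% |
| 10% / 0% | 7.6% | 4.5% |
| 15% / 0% | 16.8% | 8.0% |
| 15% / 5% | 7.8% | 4.7% |

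With access required, the three VerTouch-only rows become 1.6%, 1.8% and 2.0% (1.2%, 1.9% and 1.7% in the milder pattern). Monte Carlo error (95%) is about 0.3 points near 2.5% and 0.8 points near 21%.

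**5. If VerTouch does well.** At the 90% first-attempt success of the prior data in 6.4.1, 0.10 × 48 = 4.8 VerTouch subjects fail the first insertion. Abandoning 10–30% of them affects 0.5–1.4 subjects.

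**6. Primary endpoint, same scenarios, all stopping after one insertion.** The raw-count analysis favours VerTouch in 2.7% of null trials with no abandonment, 2.7% at 10%/10%, 0.9% at 5%/10%, and 5.8%, 12.0% and 21.3% at 5%, 10% and 15% in VerTouch only. Giving each failed case its own total plus 1 turns the last three into 4.1%, 6.1% and 8.9%. Giving failed cases the highest observed count turns them into 0.7% or less, but raises the 5%/10% scenario from 0.9% to 7.6%.

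**The case against.** The strongest reply is that 7.4.1 is a data-collection list and the definitions are in 6.3.2. A case stopped after a failed insertion did require another, and the sample-size text speaks of success. On that reading the plan already excludes it. This largely stands as evidence of intent, so a reader who infers that the plan settles on calling failed procedures successes goes further than the documents do. But no text names access, and the one operational rule omits it. The Visit 1 flowchart (protocol Figure 6) and the eCRF are not available here and could carry a rule.

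Second, the larger figures assume abandonment in VerTouch only. A reader might use the Background's radiology referral rate above 47% in settings such as emergency medicine to support them. It does not. Its base is unclear, and it describes practice in general. Applied to the 50% of emergency cases failing the first insertion, with emergency medicine one third of each arm, it gives 0.47 × 0.5 × 16 = 3.8 of 48 in each arm alike. That resembles the equal-abandonment row, which shows no inflation. The exclusions for high BMI, lumbar surgery, prior failed neuraxial anesthesia and spinal deformity may remove some hard cases. Protocol 9.2.1 also allows reversion to the manual procedure, a step short of abandonment.

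Third, procedure success and referral are compared between arms. Those comparisons may reveal an imbalance, but they do not change the success flag, and Hypothesis 7 comes last in the sequence.

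**Conclusion.** The point holds as a conflict between an operational rule and the evident intent of the endpoint, with moderate confidence. Followed literally, 7.4.1 overstates first-insertion success in any arm with procedures stopped after one failed insertion, and first-pass success where there was also no redirection.

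Bias between arms needs unequal abandonment and can favour either arm. If abandonment is equal, gated Hypothesis 1 stays at about 1%. With 5–15% in VerTouch only and every case stopping after one insertion, it reaches about 3–17%. If VerTouch performs as in its prior data, the effect is small. All of these rest on assumed rates.

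A reader might also infer that the primary analysis is wrongly specified, because the stated aim is to "reduce the number of insertion attempts to successfully access the spinal canal in a spinal puncture" while a failed case stopped after one insertion scores the minimum of 1. The documents do not support that. Using raw totals whatever the outcome is an explicit and defensible choice, and success-only and per-protocol repeats are planned. A further sensitivity analysis is optional. What the primary text does leave open is counting after referral: "Attempts are counted until confirmation of spinal canal access can be assessed" does not say whether insertions made in radiology belong to the count.

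**What to change.** 1. In the synopsis, protocol 6.3.2 and 7.4.1, and SAP 8.3.4, define first-insertion success as exactly one insertion and confirmed spinal canal access, and first-pass success as exactly one pass and confirmed spinal canal access. Use the term first-insertion success in Hypothesis 1 (protocol 8.2.1, SAP 8.2). Record canal access separately from sensory block for anesthesia cases, because procedure success there is defined by the block.
2. Keep the raw-count primary analysis. Optionally add to protocol 8.2.2 and SAP 8.3.3.3 a sensitivity analysis with no decision role and the same rule in both arms. Each subject without confirmed access receives their own total plus 1 and, in a separate run, the highest observed count. Describe the second as an extreme scenario that penalises the arm with more failures. It is not a conservative bound, because it can favour VerTouch when palpation has more failures (7.6% at 5%/10%). The first only partly corrects (up to 8.9%).
3. State whether insertions made after referral to radiology are counted.

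Cost: wording changes in both documents, possibly one eCRF field, and slightly less favourable success rates in any arm with failures.
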